**Randomization Blocks:**

2 1 1 1 2 2 1 2 1 2

1 2 2 2 1 2 1 1 2 1

2 2 2 1 2 1 1 2 1 1

2 1 2 1 2 2 1 1 2 1

1 1 1 1 2 2 2 2 1 2

2 2 1 1 1 1 2 2 2 1

1 1 2 1 1 2 2 2 2 1

2 1 2 1 2 1 2 2 1 1

2 2 1 2 2 1 2 1 1 1

2 2 1 1 2 1 1 2 2 1

2 2 1 1 1 2 1 1 2 2

1 1 1 2 1 2 2 1 2 2

2 2 1 2 1 1 2 1 1 2

1 2 2 2 2 1 1 1 2 1

**1: Control**

**2: MTAD**

**Effect of MTAD as the final irrigation protocol on periapical healing after single-visit root canal treatment: a randomized controlled clinical trial**

NCT:.....

**Statistical Analysis**

The data were statistically analysed using the IBM SPSS Statistics Version 20.0 program (IBM, Armonk, NY, USA). Gender distribution according to groups was evaluated with Chi-square analysis and age distribution t-test. The Mann-Whitney U test was used to compare the differences (pre-treatment, post-treatment change) between the groups' pre-treatment and 24-month follow-up radiographs. The change in PAI scores for each group from baseline to the end of follow-up was evaluated with the Wilcoxon test. The Chi-Square test was used to compare bilateral variables (teeth with a PAI  $\leq 2$  scores 'healthy', teeth with a PAI  $\geq 3$  score 'failure') between two groups. In all tests, the statistical significance level was set at 0.05.

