## **Patient Selection**

One hundred patients with a noncontributory medical history presented to the Department of Endodontics of the University of Cukurova Faculty of Dentistry between October 2019 and February 2020 were selected according to inclusion and exclusion criteria. All selected teeth were single-rooted, maxillary and mandibular incisors, canines or premolars that were asymptomatic (no preoperative pain, swelling or acute endodontic or periodontal abscess). All pulps were nonvital and did not respond to cold testing. All patients were aged between 18 and 65 years, had no systemic diseases or allergies to local anaesthetic agents, had not previously received any endodontic treatment and had no radiographic evidence of periapical bone loss. Pregnant and breast-feeding women and patients taking analgesic, anti-inflammatory or antibiotic medications during the 7 days prior to the beginning of treatment were also excluded. All patients were informed that they were to be included in a clinical trial and their consent was obtained.

Based on the study of Verma et al., a change in PAI score of 0.50 units and above is found to be clinically significant, and at least 42 patients per group should be included at 90%

power and 5% margin of error, assuming the standard deviation of the change is 1.0. Given the possibility of dropouts throughout the study, it was planned to take 20% more and to conduct the study on 50 patients per group.

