### **Radiographic and Clinical Evaluation**

Patients were invited to follow-up sessions at 6, 12, 18, and 24 months and were radiographically and clinically assessed. Many patients missed their follow-up appointments due to the covid 19 pandemic. The follow-up radiographs performed by long-cone paralleling technique with a film holder. The pre-treatment and 24-month follow-up radiographs of teeth, were prepared as a Power Point presentation (Microsoft ® Corporation, Redmond, WA) and the change in periapical radiolucency was assessed according to PAI scores of five categories; 1. Normal apical periodontium 2. Small changes in bone structures 3. Change in bone structure with mineral loss 4. Periodontitis with well-defined radiolucent area 5. Severe periodontitis with exacerbating features. Teeth with a  $PAI \leq 2$  score and clinically asymptomatic were considered 'healthy' in the radiographic evaluation, while teeth with a  $PAI \geq 3$  and/or clinically symptomatic were considered 'failure'.

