**Results:**

In the MTAD group, 2 patients were excluded from the study due to health problems and 1 patient was excluded because of pregnancy. A total of 97 patients, 64 females and 33 males (47 MTAD, 50 Control) with apical periodontitis, were included in this study. After a 24-month follow-up, 25 of the 97 patients (15 Control and 10 MTAD) were excluded from the study because of not to attend follow-up appointments. Pre-treatment and 24-month follow-up radiographs of a total of 72 teeth, 37 in the MTAD group and 35 in the Control group, were examined and evaluated according to the PAI score.

Age and gender distribution were compatible between the groups, and no statistically significant difference was found in terms of gender (Chi-Square Test) and age (t-test) ( $P > 0.05$ ). Initial PAI scores were consistent in the teeth with periapical lesions of the patients in

the two groups, but there was no statistically significant difference between them. There was no significant difference in baseline and follow-up scores between groups ( $p=0.744$ ,  $p=0.469$  respectively). No change was observed in the PAI score of 3 patients (8.6%) in the Control group and 4 patients (10.8%) in the MTAD group. There was no statistically significant difference between the groups' post follow-up PAI scores ( $p= .551$ ).

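### The chi-square test splits teeth into 'healthy' and 'failure' by PAI alone, but the trial's own outcome definition also counts a clinically symptomatic tooth as a failure

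*Combined protocol and SAP*

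**What the plan says.** The Radiographic and Clinical Evaluation section defines a two-part outcome. A tooth needs both a low PAI and no symptoms to succeed: PAI 2 or less is followed by "score and clinically asymptomatic were considered 'healthy' in the radiographic evaluation". Either part is enough to fail: PAI 3 or more is followed by "and/or clinically symptomatic were considered 'failure". The same section describes the follow-up: "Patients were invited to follow-up sessions at 6, 12, 18, and 24 months and were radiographically and clinically assessed".

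The Statistical Analysis section tests the same two labels between the arms: "The Chi-Square test was used to compare bilateral variables (teeth with a PAI". Its parenthesis writes out both categories, PAI 2 or less as healthy and PAI 3 or more as failure, and clinical status appears in neither. The other outcome tests there also use PAI only: "The Mann-Whitney U test was used to compare the differences" (baseline against 24 months, between arms) and "The change in PAI scores for each group from baseline to the end of follow-up was evaluated with the Wilcoxon test".

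The Results section reports 72 teeth, 35 Control and 37 MTAD, evaluated by PAI score. It gives no symptom counts and no healthy/failure counts.

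**The concern.** One pair of labels has two definitions, and the analysis section uses the narrower one. Read as written, the clinical assessments made at follow-up enter no outcome analysis, although the outcome definition treats symptoms as sufficient for failure. A patient with a painful tooth and a clean radiograph would be counted as a success in the trial's only success/failure comparison.

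The error can go only one way within each arm, because dropping the symptom criterion can only remove failures. Anyone given a healthy rate from this trial could not tell which rule produced it.

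The composite is also not fully specified. The radiographs compared are those at baseline and 24 months, but clinical assessment is listed at four visits and the section does not say which visit's status counts. Nor does it say which follow-up findings make a tooth symptomatic. The Patient Selection section explains the term for entry only: "asymptomatic (no preoperative pain, swelling or acute endodontic or periodontal abscess").

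**Working it through.** **1. The two rules side by side.** The plan states no figure for this outcome, so there is nothing to reproduce. The check is to classify every combination of PAI and symptoms under each section.

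| 24-month PAI | Symptoms | Radiographic and Clinical Evaluation | Statistical Analysis |
|---|---|---|---|
| 2 or less | no | healthy | healthy |
| 2 or less | yes | **failure** | **healthy** |
| 3 or more | no | failure | failure |
| 3 or more | yes | failure | failure |

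The rules differ in one cell. In each arm, failures under the composite = failures by PAI + k, where k ≥ 0 is the number of symptomatic teeth with PAI 2 or less.

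**2. Size per tooth.** The denominators are 35 Control and 37 MTAD (Results). The change in an arm's healthy rate is k/n.

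- Control: 1/35 = 2.86 points; 3/35 = 8.57 points.
- MTAD: 1/37 = 2.70 points; 3/37 = 8.11 points.

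The documents do not give k. An assumed range of 0 to 3 teeth in one arm gives 0 to 8.6 points (Control) or 0 to 8.1 points (MTAD).

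**3. Effect on the test.** This cannot be computed for the trial, because the healthy/failure table is not given. To show the range, assume 0 to 5 PAI failures in each arm (36 starting tables, written Control v MTAD), and add reclassified teeth to one arm until two-sided p < 0.05. The Pearson statistic, without continuity correction, is N(ad − bc)² / (r₁r₂c₁c₂). For 4 v 0 this is 72 × (4 × 37 − 31 × 0)² / (35 × 37 × 4 × 68) = 4.48, p = 0.034.

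| Starting tables | Pearson: teeth needed | Fisher: teeth needed |
|---|---|---|
| Equal counts (0 v 0 to 5 v 5) | 4 to 8 | 5 to 9 |
| All tables not already significant | 1 to 12 (32 tables) | 1 to 13 (35 tables) |

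- Smallest change, Pearson: 3 v 0 (p = 0.069) becomes 4 v 0 (p = 0.034).
- Smallest change, Fisher: 4 v 0 (p = 0.051) becomes 5 v 0 (p = 0.023).
- Opposite direction: 5 v 0 becoming 5 v 1 moves Pearson p from 0.017 to 0.076 and Fisher p from 0.023 to 0.102.

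With 0 to 3 affected teeth in one arm, no equal-count table becomes significant. Only unequal starting tables are that sensitive.

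**4. What is not touched.** The Mann-Whitney and Wilcoxon tests use PAI scores and do not depend on the binary rule. The sample size rests on a change of 0.50 in PAI. The binary outcome is not named as the main result.

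**The case against.** The strongest reply is that the analysis section is shorthand. It repeats the labels and cut-offs of an outcome already defined, so its parenthesis may be an abbreviated reference back, and the earlier definition is itself placed in the radiographic evaluation. This is possible, and a lapse in wording is as plausible as a different analysis variable. But nothing in the documents says so. The parenthesis writes out both categories, and the defining sentence puts symptoms into both of them whatever evaluation it names. The conflict remains.

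The second reply is that no consequence has been shown. No healthy rate is reported, the number of affected teeth may be zero, and the sensitive tables in the illustration are lopsided. The Results section gives no sign of such imbalance: "There was no statistically significant difference between the groups' post follow-up PAI scores" (p = .551), and follow-up scores are also given as not different (p = 0.469). Those p-values do not exclude an unequal binary table, but they are a reason not to read the one-tooth cases as likely. This objection stands as a limit on weight. The case rests on the inconsistent definition and its direction, not on any claim that the conclusion would change.

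The third reply is that 24 months is the natural visit for clinical status, since the classification follows directly on the 24-month radiograph comparison. That is fair, and the fix adopts it. The lack of a follow-up definition of symptomatic is a reporting gap and secondary to the main point.

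**Conclusion.** The concern holds. The two sections classify a symptomatic tooth with PAI 2 or less in opposite ways, and the rule attached to the chi-square test can only equal or understate failures against the trial's own outcome definition. The size is 2.9 points of healthy rate per affected tooth in Control and 2.7 in MTAD. The number of such teeth is unknown; if it is zero, both rules give the same table. Whether the test result would change cannot be determined from the documents. The ranges for reclassified teeth rest on the assumed 0 to 5 PAI failures per arm, and the ranges in percentage points on the assumed 0 to 3 affected teeth. The point should be corrected because this is the only success/failure classification in the trial, but it does not bear on the PAI-change analyses.

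**What to change.** Reconcile the two sections:

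- In Statistical Analysis, define the chi-square outcome as the composite in Radiographic and Clinical Evaluation, using clinical status at 24 months.
- State which follow-up findings count as symptomatic.
- Report healthy and failure counts per arm, and the number of teeth that the PAI-only split classifies differently.
- Keep the PAI-only split if wanted, labelled as a radiographic result and not under the composite's labels.

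The cost is wording and one re-tabulation of 72 teeth, provided 24-month clinical status was recorded for them; the documents say patients were clinically assessed but not what was recorded. The healthy rate in each arm may stay the same or fall.

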**Results:**

In the MTAD group, 2 patients were excluded from the study due to health problems and 1 patient was excluded because of pregnancy. A total of 97 patients, 64 females and 33 males (47 MTAD, 50 Control) with apical periodontitis, were included in this study. After a 24-month follow-up, 25 of the 97 patients (15 Control and 10 MTAD) were excluded from the study because of not to attend follow-up appointments. Pre-treatment and 24-month follow-up radiographs of a total of 72 teeth, 37 in the MTAD group and 35 in the Control group, were examined and evaluated according to the PAI score.

Age and gender distribution were compatible between the groups, and no statistically significant difference was found in terms of gender (Chi-Square Test) and age (t-test) ( $P > 0.05$ ). Initial PAI scores were consistent in the teeth with periapical lesions of the patients in

the two groups, but there was no statistically significant difference between them. There was no significant difference in baseline and follow-up scores between groups ( $p=0.744$ ,  $p=0.469$  respectively). No change was observed in the PAI score of 3 patients (8.6%) in the Control group and 4 patients (10.8%) in the MTAD group. There was no statistically significant difference between the groups' post follow-up PAI scores ( $p= .551$ ).

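### The 24-month comparison of the arms rests on 72 completers, with no missing-data sensitivity analysis and no effect estimate or confidence interval

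*Combined protocol and SAP*

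**What the plan says.** The Statistical Analysis section names a test for each between-arm outcome. For change in PAI, "The Mann-Whitney U test was used to compare the differences (pre-treatment, post-treatment change) between the groups". For healthy versus failure it names a Chi-square test, with failure there meaning PAI of 3 or more. The section gives a significance level of 0.05. It names no analysis population, missing-data method, effect measure or confidence interval.

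The Results section gives the patient flow. In the MTAD arm "2 patients were excluded from the study due to health problems and 1 patient was excluded because of pregnancy", which leaves 97 (50 Control, 47 MTAD). Then "25 of the 97 patients (15 Control and 10 MTAD) were excluded from the study because of not to attend follow-up appointments". What was assessed is "Pre-treatment and 24-month follow-up radiographs of a total of 72 teeth, 37 in the MTAD group and 35 in the Control group". On outcome it states: "There was no significant difference in baseline and follow-up scores between groups", with p=0.744 at baseline and p=0.469 at follow-up, and a further p of .551 for post-follow-up scores. The only outcome figures by arm are the numbers with no change in PAI: 3 (8.6%) Control and 4 (10.8%) MTAD.

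The Radiographic and Clinical Evaluation section gives a reason for much of the loss: "Many patients missed their follow-up appointments due to the covid 19 pandemic". It also schedules assessments at 6, 12 and 18 months, and it defines failure more widely than the analysis section does, as PAI of 3 or more "and/or clinically symptomatic were considered 'failure".

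**The concern.** Three gaps meet in the one comparison that the trial was run to make.

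- **Missing patients.** More than a quarter of those apparently allocated do not contribute. The sample-size text foresaw dropout, but only by recruiting more: it required 42 per group and took 50. Nothing says how the result might depend on those who did not return.
- **No estimate.** A non-significant p-value does not say how large a difference remains compatible with the data. A reader cannot tell a trial that found little difference from one too imprecise to find it.
- **Two failure definitions.** A tooth with PAI of 2 or less and clinical symptoms is a failure in the evaluation section but not in the analysis section. Any healthy/failure result, and any sensitivity analysis built on it, depends on which rule was applied.

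What is at stake is how much weight the reported absence of a difference can bear.

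**Working it through.** **1. The plan's own figure.** Inputs from Patient Selection: change 0.50, SD of change 1.0, power 90%, alpha 5% (taken as two-sided; the text does not say). The one-sample formula gives ((1.960+1.282)×1.0/0.50)² = 42.03, which matches the stated 42. The two-arm formula doubles this to about 84, or 85 per arm after rounding up. So 42 fits a within-arm change and not a between-arm difference. This bears on how 0.50 may be used in step 3.

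**2. Loss.** The split of 50 per arm is inferred from 100 selected, 50 planned per group, 50 Control and 47+3 MTAD.
- Control: 50−35 = 15, or 30%.
- MTAD: 50−37 = 13 (3 exclusions and 10 non-attenders), or 26%.
- Total: 28 of 100. Going from 50 to 42 would have allowed 8/50 = 16%.
- Fisher, 15/50 v 13/50: p=0.82. Exclusions, 0/50 v 3/50: p=0.24.

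**3. Precision on the PAI scale.** Half-width = t(0.975, n₁+n₂−2) × SD × √(1/n₁+1/n₂), with SD 1.0:

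| Control v MTAD | t | √(1/n₁+1/n₂) | Half-width |
|---|---|---|---|
| 50 v 50 | 1.984 | 0.200 | 0.40 |
| 42 v 42 | 1.989 | 0.218 | 0.43 |
| 35 v 37 | 1.994 | 0.236 | 0.47 |

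The loss adds about 0.07; the other 0.40 was built into the design. SD 1.0 is a planning value and the half-width scales with it: 0.470×0.75 = 0.35 at SD 0.75, and 0.470×1.25 = 0.59 at SD 1.25. If 0.50 is read as a between-arm difference (an assumption), then at SD 1.0 power at 35 v 37 is 0.55. Differences of 0.50 in both directions are then excluded only when the observed difference is within 0.50−0.47 = 0.03 of zero. Excluding one direction alone is easier.

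**4. The one outcome with counts.** No change in PAI: 4/37 − 3/35 = +2.2 percentage points, Newcombe 95% CI −13.0 to +17.2. This is not the endpoint, but it shows how wide an interval 72 teeth give.

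**5. Tipping point on healthy/failure.** The Results give no failure counts, so completer failure rates are assumed, about equal in the two arms, with missing Control patients failing at about that rate. Denominators are 50 v 50. The last two columns give the MTAD failures needed among the 13 missing for p<0.05 with MTAD worse.

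| Assumed rate | Completer failures (Control, MTAD) | Missing Control failures (of 15) | Uncorrected Chi-square | Fisher or corrected Chi-square |
|---|---|---|---|---|
| 5% | 2, 2 | 1 | 8 | 9 |
| 10% | 4, 4 | 2 | 10 | 11 |
| 20% | 7, 7 | 3 | 12 | 13 |
| 30% | 10, 11 | 4 | 13 | none |
| 40% | 14, 15 | 6 | none | none |

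Of the 16×14 = 224 possible combinations, 61, 51, 39, 31 and 30 (uncorrected) or 45, 37, 29, 21 and 20 (Fisher or corrected) reach p<0.05 in either direction. The version of Chi-square matters and is not stated.

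Best and worst case run from (Fm−Fc−15)/50 to (Fm+13−Fc)/50, where Fm and Fc are MTAD and Control completer failures. That is −30 to +26 points for 5–20%, and −28 to +28 for 30–40%.

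**The case against.** The strongest case against the point is that nothing suggests harm from the loss. Rates are close, the pandemic is a plausible cause unrelated to the irrigant, and non-attenders have no 24-month film, so analysing completers was the natural default. This largely stands, and it rules out any claim of demonstrated bias. It does not remove the point. The pandemic is given as the reason for many missed visits, not all. Similar rates do not establish similar reasons, and the three exclusions for health or pregnancy are all in MTAD, though that could be chance.

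Second, a reader might infer that the trial failed to exclude a difference that the protocol itself calls important. The documents do not support that. The 0.50 is described as a change in PAI, and 42 is reproduced only by a one-sample formula; no between-arm margin is stated. The half-width of 0.47 is sound as a statement of precision at SD 1.0, but setting it against 0.50 is an assumption.

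Third, a reader might blame the imprecision on both arms finishing below 42. That also fails: the half-width would already have been 0.40 with everyone followed.

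Fourth, the tipping-point table above uses assumed failure rates and treats all 28 patients as wholly unknown, although some may have been seen at 6, 12 or 18 months. This stands, and the sponsor's own table should use actual counts and any such visits.

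**Conclusion.** The point holds as a reporting and sensitivity-analysis gap that should be closed. The 24-month comparisons use 72 of an inferred 100 allocated patients, no sensitivity analysis covers the other 28, and the between-arm PAI results at 24 months are p-values alone (0.744 is the baseline comparison). The healthy/failure endpoint also has two definitions, and no failure counts by arm are given.

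The best-case and worst-case limits of nearly 30 points either way may tempt a reader to call the null unreliable. They are arithmetic consequences of a 28% loss, not evidence of bias. On the assumed rates, roughly 8 or more of the 13 missing MTAD patients would have to fail while missing Control patients failed at the ordinary rate. At 40% failure no number would be enough.

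These conclusions rest on the inferred 50/50 allocation, two-sided tests, SD 1.0 for the half-width, and the assumed failure rates. The arithmetic of the loss and the absence of an estimate or interval need only the documents' own text.

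**What to change.** Keep the Mann-Whitney test on change and add the following, labelled post hoc because results are already reported.

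1. **Estimate.** Report the between-arm difference in PAI change with its 95% CI on the PAI scale, adjusted for baseline PAI. This still uses completers, but if the model holds it is valid when loss depends only on arm and baseline PAI. A proportional-odds odds ratio may be shown as a supplement; alone it would not say what difference in PAI units is excluded.
2. **Endpoint.** Reconcile the failure definitions in Radiographic and Clinical Evaluation and in Statistical Analysis, state which was used, and report healthy/failure counts by arm. Do this before item 3.
3. **Sensitivity.** Give a tipping-point table over all 28 missing patients (0–15 Control by 0–13 MTAD failures), using the actual completer counts and any 6-, 12- or 18-month assessments that non-attenders have. Show best and worst case as arithmetic limits. Say whether the Chi-square is corrected, with Fisher beside it.

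The cost is one model, one table and a few lines of text, with no new patients, visits, films or PAI scoring. The drawbacks are post hoc status and model assumptions on a scale with few categories. The precision gain from adjustment is uncertain. Relative to unadjusted change, the variance ratio is (1−r²)/(k²+1−2rk), where r is the baseline to follow-up correlation and k the ratio of baseline to follow-up SD. At k=1 it is 0.60, 0.70 and 0.80 for r = 0.2, 0.4 and 0.6. Against a 0.50 difference (the assumption made above), power would move from 55% to 77%, 71% and 65%. When r equals k there is no gain. Neither quantity is reported.
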